**Aim 2 (Exploratory): To explore the effects of switching to VLNCCs plus ECIG-Hi or ECIG-Lo nicotine doses on abuse liability using biochemical measures of product use, compensation, and toxicant exposure, and self-reported measures of withdrawal, craving, affect, and satisfaction.** On an exploratory basis, we will examine the differences of ECIG dose (VLNC+ECIG-Lo vs. VLNC+ECIG-Hi) on additional measures of abuse liability, including ECIG puff count, withdrawal, craving, negative affect, minor tobacco alkaloid (MA) levels, acrolein DNA adduct levels, expired CO, RRE (i.e., purchase tasks), and liking (implicit attitudes, perceived harm, product satisfaction ratings).

**Aim 3 (exploratory): To explore the effects of switching from usual-brand cigarettes to VLNCCs, and from VLNCCs to VLNCC+ECIGs on measures of abuse liability.** On an exploratory basis, we will examine potential changes in the abuse liability measures from Aims 1 & 2 between the UB cigarette and VLNCC only phases, and between those phases and the dual-use phases (VLNC+ECIG-Lo and VLNC+ECIG-Hi).

**Aim 4 (exploratory): To characterize the effects of dual use of VLNCC and JUUL ECIGs on abuse liability.** On an exploratory basis, we will examine the differences in measures of abuse liability between the two phases of dual-use (VLNC+JUUL-Lo vs. VLNC+JUUL-Hi) among participants assigned to the JUUL ECIG arm.

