**Assessment of nicotine abuse liability.** We will be measuring abuse liability using multiple domains. In terms of the 5 abuse liability domains described by Carter and colleagues , we will be capturing 4, including acute dose-effect comparisons (ECIG-Hi vs. ECIG-Lo), suppression of withdrawal and craving (in-session withdrawal and affect questionnaires; EMA measures of withdrawal, craving, affect), self-administration (RRE; nicotine compensation: TNE, MA, expired CO), and choice procedures (product choice between VLNCC and ECIG during dual use phases). For Aims 1 and 2, we will assess abuse liability in terms of nicotine compensation (i.e., urinary TNE and MA, expired CO) and product use, product liking (i.e., implicit attitudes, perceived harm, satisfaction), and RRE (i.e., purchase task valuation) at the end of each study phase. To assess product use for Aims 1 and 2, participants will be provided with smartphones prior to the start of phase 2 for once daily recording of CPD (also a primary outcome) and e-cigarette use (puff counts from device). For Aim 3, we take a multi-modal approach to the measurement of withdrawal, craving, affect and satisfaction (reinforcement) which provides progressively more sensitive assessments that range from traditional measures (questionnaires filled out weekly) to the smartphone daily diary (patients overall assessment of the day) to real-time measures captured through EMA. Questionnaires will be administered at each of the 5 in-person sessions, smartphone daily diary will be collected during phases 2, 3, and 4, and smartphone EMA assessments will be conducted in phases 3 and 4 only.

**COVID-19 adaptation:** Enrolled participants will be mailed free study smartphones prior to the start of phase 2 to be used for the duration of their participation in the study.

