**In-person screening session.** Participants will be instructed to smoke *ad libitum* prior to this session. They will complete basic demographic, health and smoking history questionnaires used in our previous studies that will be reviewed and approved for eligibility by a licensed medical provider. Tobacco product consumption rates will be established using a timeline follow back procedure [95] and smoking history measures used in previous studies [70]. Psychiatric stability, including suicidality criteria, will be assessed using the PHQ-9 [96], a measure of depressive and suicidality symptoms, and the GAD-7 [97], a measure of anxiety symptoms. We will also assess nicotine dependence (Fagerström Test for Nicotine Dependence; FTND) [98] and expired CO. Any individual who is deemed ineligible for study participation for medical/psychiatric reasons will be referred to local medical and/or psychiatric resources. Any participant who spontaneously reports mood, hopelessness, anxiety and/or other symptoms suggesting a persistent change in mood, or who expresses suicidality, will activate the mental health procedures described in Appendix Z.

COVID-19 adaptation: Eligible participants will be scheduled for a virtual “in-person” screening session using an institutionally approved platform, such as Zoom.

**Phase 1: Baseline (week 1).** During this phase, participants will be instructed to smoke their usual brand *ad libitum*.

COVID-19 adaptation: No adaptations needed.

**Phase 2: VLNCC only (weeks 2-4).** During Phase 2, participants will be instructed to smoke only the VLNCCs provided by the study. At the beginning of this phase, they will be given 3 weeks' worth of VLNCCs (150% of their baseline usual brand amount). Regular or menthol will be provided according to their preference. While participants will be asked to use study cigarettes exclusively, they will not be penalized for smoking non-study cigarettes and will be asked to report any such use throughout the study. However, a specific, biochemically verified compensation plan related to VLNCC use will facilitate compliance and honest reporting, as described in the compensation and compliance section below. Smartphone diary assessments as described below will begin during Phase 2. A check-up call may be conducted around 3 days after the start of Phase 2 to troubleshoot any problems the participant may have in terms of starting a new study product. This will allow staff to address any issues that a

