## Measures

**In-person assessment of product use, smoking behavior, and withdrawal.** At each in-person or virtual session, participants will provide a urine sample to measure TNE and MA, and provide expired CO (except at screening, where urine for TNE/MA is not collected because participants are not on study product yet). If the session is conducted virtually, expired CO will not be collected. Research assistants will also complete a Time Line Follow Back (TLFB [99]) interview to record nicotine product use up to 30 days before screening and/or up to and including last contact, including CPD (VLNCC and own brand) and number of e-cig sessions per day. The *primary* measure of CPD will come from the daily diary data. TLFB will be used as a secondary source to supplement missing data. Participants will be required to return used and unused VLNCC packs and e-cig cartomizers at each session for compliance/accounting analysis. Cartomizer weight, before distribution and upon return will provide an estimate of total product use, which will be used in conjunction with the diary data. Participants will also complete a computerized battery of questionnaires, including nicotine withdrawal (Minnesota Nicotine Withdrawal Scale; MNWS [100]), craving (Questionnaire of Smoking Urges-Brief; QSU-Brief [101]) and affect (Positive and Negative Affect Scales; PANAS [102]). Unlike the diary data which is obtained daily, or the EMA assessments that occur in real-time, these questionnaire measures cover broader segments of time (i.e., past 7 days). Missing assessments or items are expected and acceptable and are not considered a protocol deviation/violation.

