provide measures of product use (CPD; e-cigarette puff count from device), withdrawal, craving, affect and satisfaction (reinforcement). The other is a random EMA assessment that will occur twice a day and will provide real-time measures of these same constructs (see Appendix II). To limit assessment burden, once daily diary assessments will occur in phases 2, 3, & 4, whereas by design, the user initiated and random EMA assessments occur only in phases 3 & 4. In the U54 preliminary study, an interactive voice response system was used to collect daily CPD. Here, we use the smartphone-implemented diary to collect CPD because we believe that it will provide superior reliability, as well as other advantages described below. The random EMA assessments are limited to phases 3 & 4 because our *primary* interest in these assessments is to longitudinally explore withdrawal, craving, affect and satisfaction related to dual product use among DS and ITS, including the differential effects of ECIG dose. EMA while smoking regular cigarettes has been thoroughly studied in DS and ITS by Shiffman and colleagues [70, 71, 73, 75, 76] and need not be replicated here.

Our smart phone assessments are modeled after several of our previous studies in which we enrolled very diverse smoking populations [88, 90, 94]. We will make modifications to accommodate the ITS as outlined by Shiffman [70, 73] and provide training to participants relevant to each assessment type and study phase (see Appendices PP and RR).

The daily diary assessments will occur 30 minutes after waking and will assess 6 measures from the previous day, including CPD (VLNCC/UB), 8 items based on the QSU, PANAS and MMWS to assess withdrawal, craving, affect (negative and positive) and satisfaction. For the random EMA assessments (phases 3 & 4 only), participants will be prompted to complete up to 2 assessments associated with product use (based on smoking rate-see below). To enhance compliance, the smartphone will provide immediate feedback, as described in the compensation section below.

For the random assessments, each day will be divided into 2 blocks. Within each block, 1 EMA assessment will be randomly triggered to assess withdrawal, craving, affect, and reinforcement. The software prevents random assessments from occurring within 15 minutes of other assessments. Because prompts may occur at inconvenient times, participants can choose to not participate in that random assessment.

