Another potential issue is that the length of the phases may be insufficient to sample ITS smoking behavior. However, Shiffman and colleagues, who have done the most sophisticated work with this population, have used a 21-day (3 week) sample in EMA studies [73]. Additionally, it may be difficult to estimate the "typical" TNE and MA among ITS given their low frequency of smoking. To address this, we collect urine samples twice per week (in Phases 2, 3, and 4) to better estimate these compounds among ITS, and like Shiffman and colleagues [8], we will select for analysis the sample that most closely corresponds in time to smoking their median CPD from Phase 1. If the participant fails to bring in any/all samples, a deviation will not be logged. A spot urine collection will be conducted during the visit in the event no samples are returned.

Finally, rather than conduct random EMA assessments for the entire duration of the study, which would quite burdensome to participants, we have elected to conduct daily diary assessments (once per day) in phases 2-4 and to implement random (up to 2 times per day) assessments only in phases 3 & 4. We feel this is a reasonable trade off to reduce participant burden since our primary interest in the EMA data pertains to the assessment of frequency and circumstances surrounding dual product use. In addition, EMA information during regular smoking has been thoroughly explored for DS and ITS by Shiffman and colleagues [70, 71, 73, 75, 76].

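### The main cigarettes-per-day source, the daily diary, starts in Phase 2, so the exploratory Aim 3 usual-brand contrasts set Phase 1 recall-interview counts against mainly diary counts

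*Combined protocol and SAP*

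**What the plan says.** **Source of CPD.** Under Measures, the primary "measure of CPD will come from the daily diary data. TLFB will be used as a secondary source to supplement missing data". TLFB is described there as an "interview to record nicotine product use up to 30 days before screening and/or up to and including last contact", so it reaches back before Phase 1 and runs through every later phase. Table 4 and the abstinence paragraph under Assessments and Questionnaires also place TLFB at every visit.

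**When the diary runs.** Four places agree.
- Study overview: "participants will be provided with smartphones prior to the start of phase 2 for once daily recording of CPD".
- Procedures, Phase 2: "Smartphone diary assessments as described below will begin during Phase 2".
- Measures, smartphone assessments: "once daily diary assessments will occur in phases 2, 3, & 4".
- Potential Problems & Alternative Strategies: "we have elected to conduct daily diary assessments (once per day) in phases 2-4".

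**What is compared.** Aim 1, the only aim with a stated hypothesis, compares the high- and low-dose e-cigarette phases. Aim 3 is exploratory: "we will examine potential changes in the abuse liability measures from Aims 1 & 2 between the UB cigarette and VLNCC only phases". It also sets each of these two against dual use. CPD is one of the Aim 1 measures. The Aim 3 analysis is a mixed model with all four phases as levels.

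The documents name no CPD source for Phase 1, no rule for combining the two sources across phases, no same-source analysis and no diary/TLFB comparison.

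**The concern.** Phase 1 has no diary by design. If TLFB fills the gap, all usual-brand counts are interview recall and later counts are mainly diary. The switch of instrument then coincides with the switch of product, and the model cannot separate them. Any systematic difference between the instruments goes straight into the estimated change in smoking from usual brand, and a larger sample does not reduce it.

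These are the trial's only estimates of how far CPD moves from usual-brand smoking, so their size will be read with interest even though the aim is exploratory. TLFB already exists in every phase, so a like-for-like comparison is available and is simply not specified.

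**Working it through.** **Step 1. CPD source by phase.**
- Phase 1 (usual brand): TLFB only.
- Phases 2, 3 and 4: diary, with TLFB filling missing days.

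That Phase 1 rests on TLFB is an inference, since no sentence says so directly. It is a firm one, because no other CPD source is named for that week.

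**Step 2. Check against the payment schedule.** The compensation section pays $2 per diary and $3 per momentary assessment (up to two a day, Phases 3 and 4), with a cap of $378 for smartphone assessments.
- Diary in Phases 2 to 4: 63 days x $2 + 42 days x 2 x $3 = $126 + $252 = $378. This matches.
- Diary in Phases 1 to 4: 70 x $2 + $252 = $392. This does not.

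**Step 3. Reproduce the planned effect (Table 1 means, Table 2 risk ratios).**
- Daily smokers: 14.19 / 19.62 = 0.723; fall 19.62 - 14.19 = 5.43 CPD.
- Intermittent smokers: 2.47 / 3.42 = 0.722.
- Both match the 0.72 in Table 2.

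**Step 4. Illustrate an instrument difference.** Let k be the TLFB/diary ratio. Observed Phase 1 CPD is k x the Table 1 value, and the observed risk ratio is the true one divided by k. The documents give no k; 0.90 to 1.10 is assumed.
- Daily smokers, k = 0.90: Phase 1 = 17.66, fall = 17.66 - 14.19 = 3.47, ratio = 0.804.
- Daily smokers, k = 1.10: Phase 1 = 21.58, fall = 7.39, ratio = 0.657.
- Error in the fall: 0.10 x 19.62 / 5.43 = 36% either way.
- Daily smokers, usual brand v dual use: 12.80 / 19.62 = 0.652, observed as 0.725 to 0.593.
- Intermittent smokers: 0.722 / 0.90 = 0.802; 0.722 / 1.10 = 0.657.

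**Step 5. What this does to the intermittent-smoker test.** Table 2 gives a minimum detectable risk ratio of 0.76 at 82% power. Assume two-sided alpha 0.05 and a normal approximation.
- Implied SE of log ratio: 0.274 / (1.960 + 0.915) = 0.095.
- Critical ratio: exp(-1.96 x 0.095) = 0.83.
- At k = 0.90: |log 0.802| / 0.095 = 0.220 / 0.095, about 2.3, so the expected estimate is still significant. Power is the normal probability below 2.305 - 1.960 = 0.345, about 64%. Table 2 states 93.9% with no instrument difference.
- k at which the expected estimate just reaches the critical ratio: 0.722 / 0.83 = 0.87, outside the assumed range.

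**The case against.** The best defence is about weight. The issue touches one outcome, in one set of contrasts, in an aim labelled exploratory. The diary schedule is a stated choice to limit burden. For change from baseline, the plan names total nicotine equivalents (TNE) as its primary measure of compensation, and TNE does not come from the diary. All of this stands, and it is why the point is minor.

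A second defence is that no bias has been shown. The diary is itself retrospective: it asks each morning about the previous day. Both instruments are day-level self-report that differ in recall length and mode, and screening consumption is already established by TLFB. This also stands. The documents establish the confounding, not a bias of known size, and the 36% above only rescales the assumed ratio.

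A third is that TLFB-only contrasts may not be clean either, since keeping a diary may aid recall in Phases 2 to 4 but not in Phase 1. That is fair. A same-source analysis reduces the measurement difference without necessarily removing it, so it should sit beside the mixed-source estimate rather than replace it.

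Stronger readings are tempting and are not supported.
- *The primary comparison is compromised.* It is not. Both Aim 1 phases, and the very low nicotine v dual-use contrasts, have the diary as main source on each side.
- *Table 2 mixes the sources.* Its effect sizes come from data in the earlier low-nicotine cigarette trial.
- *A ratio just below 0.95 (0.722 / 0.76) would overturn the intermittent-smoker result.* The 0.76 is the effect detected with 82% power, not a significance threshold.
- *TNE is biased too.* For intermittent smokers, "we will select for analysis the sample that most closely corresponds in time to smoking their median CPD from Phase 1", and the CPD source for that matching is unstated. But no effect on TNE can be shown, and participants seen virtually give a single sample per visit. It is a missing detail, not a demonstrated bias.

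**Conclusion.** The point holds as a minor one. Run as written, every Aim 3 CPD contrast against usual brand compares Phase 1 TLFB with mainly diary counts, so instrument and phase cannot be separated. This rests on TLFB being the Phase 1 source, which the named sources and the payment cap support.

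The size is unknown. Under the assumed ratio of 0.90 to 1.10, the estimated fall in daily smokers could be about a third too small or too large. In intermittent smokers the cost at 0.90 is lost power rather than a changed expected conclusion. The power figure takes Table 2's own precision at face value. Usual brand always comes first, so these contrasts would remain limited by order even with one instrument.

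**What to change.** Add a few sentences to the Aim 3 analysis.

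1. State the CPD source for Phase 1 and for each contrast.
2. For CPD contrasts involving Phase 1, add an analysis using TLFB in all phases over a window of the same length before each visit, for example the last 7 days. Fixing the window matters because visit spacing is flexible.
3. For intermittent smokers, repeat it as a check with a 21-day window of equal length in every phase. For Phase 1 this takes in usual-brand days before that phase, which TLFB can cover.
4. Report this beside the mixed-source estimate, with diary/TLFB agreement in Phases 2 to 4.
5. Keep the diary as the source for contrasts among Phases 2 to 4, including Aim 1.

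No new data are needed. The costs are a second CPD model, with Phase 2 CPD reported from two sources, and reliance on longer recall. Intermittent smokers also contribute few smoking days to a 7-day window: at 4 to 27 days a month, 7 x 4/30 = 0.9 to 7 x 27/30 = 6.3, against 2.8 to 18.9 in 21 days. Any aid to recall from diary keeping in Phases 2 to 4 would remain.

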Participants randomized to the JUUL arm will be provided with the same weekly allocation of VLNCCs as in phase 2, as well as a supply of JUUL e-cigs. During these phases, participants will be encouraged to freely use any combination of the VLNCCs and their assigned JUUL product, JUUL-Hi or JUUL-Lo, randomized within-subjects by phase (i.e., Phase 3: JUUL-Hi, Phase 4: JUUL-Lo; or Phase 3: JUUL-Lo, Phase 4: JUUL-Hi). Each participant will receive JUUL Device Kits (2 rechargeable JUUL devices and 2 USB chargers), a supply of JUULpods to last to the next laboratory session (one pod/day), and a user manual. The JUUL-Hi and JUUL-Lo JUULpod cartomizers will contain 1 ml of 59 mg/ml or 36 mg/ml nicotine solution, respectively, in the flavor (tobacco or menthol) of each participant's choice.

At the beginning Phase 3, participants will receive training in how to use the ECIG product. They will participate in hands-on training that will include e-cig assembly (battery and cartomizer), turning the cartomizer on and off, puffing, and recharging the battery. The training session will include a minimum of three bouts of 10 puffs each in which the user will be encouraged to vary puff topography to maximize desired sensory qualities of product use. Participants will be able to try and choose from tobacco, fruit, cream, or menthol flavored nicotine solutions (see Appendix JJ). This procedure is similar to what is used in the P50 TCORS led by our co-investigator [name]. A check-up call may be conducted around 3 days after the start of Phase 3 to troubleshoot any problems the participant may have in terms of starting a new study product. Participants are asked to bring all ECIG products back at each applicable visit whether used or unused for purposes of accounting (see Appendix LL).

Participants and study staff will be blind to ECIG nicotine dose condition. The eGo cartomizers will be shipped from the vendor to the study Program Director at MD Anderson and then taken over to Greenpark Pharmacy or will be shipped directly to Greenpark, who will fill them with the appropriate volume, concentration, and flavor of nicotine solution. Senior staff that are unblinded (i.e. do not have direct patient contact) will store and manage the inventory and labeling of blinded products. Study staff will distribute the product to patients at each visit. The nicotine solution will be procured through AVAIL Vapor, LLC and shipped to the study Program

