Director at MD Anderson and then taken over to Greenpark Pharmacy or will be shipped directly to Greenpark following quality assessment for nicotine concentration using GCMS. Returned or unused study product will be destroyed per institutional guidelines. Avail Vapor and other comparable vendors will supply the e-liquid for use in the eGo ECIG. We will purchase the JUUL devices and JUULpods from a local retailer.

**COVID-19 adaptation:** Participants will be mailed their 3-week allotment of study ECIGs and VLNCCs prior to the start of phases 3 and 4 by a study staff member blinded to the nicotine dose.

**30 Day Follow up Phone Call** Participants will receive a follow-up phone call between ideally 30 and 45 days after the final clinic visit (or scheduled Visit 4 completion date) to assess any open AEs and to complete Timeline Follow-Back since their last visit, however, the end of the window will not close until Timeline Follow-Back is collected or the study ends, whichever is sooner. If the participant became pregnant during the study, this would have been recorded as an adverse event. During this phone call, the research assistant will confirm her due date. This event will remain open until delivery. At that time, the licensed medical professional will contact the participant to ask a few questions about the baby's health and will update the Adverse Event.

**COVID-19 adaptation:** No adaptions required.

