COVID-19 adaptation: Participants also will be asked to collect a urine sample at home on or near the day of their virtual "in-person" visits, starting at Visit 1. For ease of remote collection, we will only ask for participants to complete one urine collection on or near the time of their visit. We will provide postage-paid supplies for participants to ship these samples to the study team for proper storage and analysis.

Total Nicotine Equivalents (TNE) is the sum of total nicotine, total cotinine, total 3'-hydroxycotinine and nicotine N-oxide excreted in urine ("total" refers to the analyte and its glucuronide conjugate) comprise 85 to-95% of the nicotine dose received by a tobacco user [118], and is an excellent biomarker of nicotine uptake, directly measuring a high percentage of the nicotine dose. TNE will be analyzed by liquid chromatography-electrospray ionization-

tandem mass spectrometry (LC-ESI-MS/MS) [119, 120]. Use of TNE will enable us to quantify changes in nicotine exposure through each phase of the study and will be *our primary measure of nicotine compensation between baseline and subsequent conditions*.

Minor Tobacco Alkaloids (MA) will be analyzed using the LC-ESI-MS/MS method [121, 122]. While nicotine is accepted as the major addictive compound in tobacco, several other constituents, such as MA (e.g., anabasine, anatabine, and nornicotine), may also play a role, and the potential differences in these compounds as a function of ECIG and VLNCC use is of interest. *MA will allow us to estimate differential use in combustible vs. e-cig use, and anatabine will allow us to determine smoking of VLNCC vs. UB.*

Quality Control Procedures. Multiple urinary aliquots will be prepared, labelled, and frozen. With each set of samples, 2 aliquots are analyzed. If the results from these 2 aliquots do not agree within 10% of the known amount, then that set of samples is reanalyzed. Negative controls are also included with each set analyzed.

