Acrolein DNA Adduct. A supplement was originally approved to quantify the formaldehyde DNA adduct N-hydroxymethyldeoxyadenosine (N-HOMe-dAdo) in leukocyte DNA samples collected using cheek swabs, but this was changed to the acrolein DNA adduct 8R/S-3-(2'-deoxyribos-1'-yl)-5,6,7,8-tetrahydro-8-hydroxypyrimido[1,2-a]purine-10-(3H)-one ( $\gamma$ -OH-Acr-dGuo) after instrumentation problems experienced by our collaborator. Measuring this acrolein DNA adduct would provide us with a measure of carcinogenesis specific to e-cigarettes [123]. It would complement the biomarkers of combustible tobacco and nicotine exposure that are included as part of this original funded R01, including total nicotine equivalents (TNE; the sum of nicotine, cotinine, 3'-hydroxycotinine and their glucuronide) and minor tobacco alkaloids (MA; i.e., anabasine, anatabine, and nornicotine). A cheek swab will be collected at Visits 1, 2, 3, and 4. Saliva samples will be sent to the University of Minnesota for analysis. Samples will be de-identified containing only the subject ID generated by the study database, visit number, code corresponding to type of sample, vial number, and date collected (e.g., 456123-03-2-5 9/1/2018).

**COVID-19 adaptation:** Participants will be asked to collect a saliva and/or cheek swab sample at home on or near the day of their virtual "in-person" visits 1, 2, 3, and 4. We will provide postage-paid supplies for participants to ship these samples to the study team for proper storage and analysis. Pending approval by MD Anderson's Research COVID Leadership Team (RCLT), community participants who can provide saliva mouthwash and/or cheek swab sample at an approved collection site will be asked to do so within a week of their scheduled virtual "in-person" visits 1, 2, 3, and 4. Approved sites may include University of Texas MD Anderson, University of Texas sister institutions, other universities or hospitals located in Texas, and/or contracted commercial vendors. Until approval is provided we will suspend collection of these samples, but continue all other aspects of the study.

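### For virtual visits the collection windows let a biomarker sample be taken after the product switch, and no rule says which phase such a sample belongs to

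*Combined protocol and SAP*

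**What the plan says.** The Study overview and the paragraph on assessment of nicotine abuse liability place the urinary measures at the end of each phase. Phases 3 and 4 follow directly on each other (weeks 5-7 and 8-10).

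**In-person visits.** Under Procedures, "Study staff will distribute the product to patients at each visit". Under Sample collection and biomarker analyses, urine is taken at each visit from Visit 1, and home samples are collected twice a week between visits.

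**Virtual visits, urine.** The COVID-19 adaptation replaces this scheme. Participants are "asked to collect a urine sample at home on or near the day of their virtual" visit, and "we will only ask for participants to complete one urine collection on or near the time of their visit". No number of days, no direction and no condition about the next product is given.

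**Virtual visits, product.** "Participants will be mailed their 3-week allotment of study ECIGs and VLNCCs prior to the start of phases 3 and 4". The Phase 2 cigarettes are likewise mailed before that phase.

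**Virtual visits, swab or saliva for the acrolein adduct.** There are two routes. At home, participants are to "collect a saliva and/or cheek swab sample at home on or near the day of their virtual" visit. At approved collection sites, those able to attend "will be asked to do so within a week of their scheduled virtual" visit. The site route is pending approval, and "Until approval is provided we will suspend collection of these samples".

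**Labels and analysis.** Sample labels carry the visit number and the collection date, but no time. The Statistical Approach specifies a mixed model for the effect of e-cigarette dose on TNE. It has no rule linking a sample's collection date to the product then in use.

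**The concern.** The visit is the boundary between two products. Table 4 puts Visits 1 and 2 on study days 8 and 29 and the check-up calls on days 11 and 32, three days later in each case. Procedures describes the same calls as about three days after the start of Phases 2 and 3. A sample taken near a visit can therefore fall on either side of a switch.

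At Visit 3 the switch is between the two e-cigarette doses. A sample collected after it, if counted as Phase 3, puts both of that participant's TNE values on the same dose, and the expected paired difference becomes zero. The error is directional: it shrinks the Aim 1 Hi v Lo contrast whichever sign that contrast has. The exploratory JUUL dose contrast in Aim 4 relies on the same visit.

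A late sample at Visit 1 mixes usual brand with VLNC cigarettes, and a late sample at Visit 2 mixes VLNC cigarettes with dual use. Both bear on exploratory Aim 3. After Visit 4 there is no next dose, but a late sample may reflect use after study product supply has ended.

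In virtual mode there is one sample per visit, so no earlier sample from the same phase can replace a late one.

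**Working it through.** **Inputs.** From Table 1, log(TNE) for daily smokers is 3.60 (SD 1.28) on Hi and 2.72 (SD 1.62) on Lo; for intermittent smokers it is 3.07 (0.80) and 2.31 (1.29). From the Power analysis, the correlation between adjacent phases is 0.4, n = 67 per group and alpha = 0.05. Sidedness is not stated, so I take two-sided.

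**Step 1: reproduce the plan's figures.** d_z = (mean Hi − mean Lo) / √(SD_Hi² + SD_Lo² − 2 × 0.4 × SD_Hi × SD_Lo).

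- Daily: variance = 1.638 + 2.624 − 1.659 = 2.604; d_z = 0.88 / 1.614 = 0.55. Paired t-test power at n = 67 is 99.3%.
- Intermittent: variance = 0.640 + 1.664 − 0.826 = 1.479; d_z = 0.76 / 1.216 = 0.625. Power is 99.9%.

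Table 2 gives 0.55 and 0.63 in absolute value, each with at least 99% power, so the planned figures reproduce.

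**Step 2: let a share p of Visit 3 samples fall after the switch.** Assume each such sample fully reflects the new dose, is counted as Phase 3, and that Visit 4 samples are correct. Those pairs have expected difference zero. Taking the within-pair variance as unchanged, for daily smokers:

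- mean difference = 0.88 × (1 − p)
- variance = 2.604 + p(1 − p) × 0.88²

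At p = 0.10: mean 0.792, variance 2.604 + 0.070 = 2.674, d_z = 0.792 / 1.635 = 0.48. At p = 0.20: 0.704 / √2.728 = 0.43. At p = 0.30: 0.616 / √2.767 = 0.37.

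**Step 3: power.** Power comes from 10,000 simulated two-period crossovers per scenario. Half of the participants take Hi first, each sample's SD is that of the dose it really reflects, and a paired t-test stands in for the mixed model.

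| Share p (assumed) | Daily: difference | Daily: d_z | Daily: power | Intermittent: difference | Intermittent: power |
|---|---|---|---|---|---|
| 0% | 0.88 | 0.55 | 99% | 0.76 | >99% |
| 10% | 0.79 | 0.48 | 97% | 0.68 | 99% |
| 20% | 0.70 | 0.43 | 93% | 0.61 | 98% |
| 30% | 0.62 | 0.37 | 85% | 0.53 | 92% |
| 50% | 0.44 | 0.27 | 57% | 0.38 | 69% |

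On the ratio scale, the daily-smoker Hi/Lo ratio goes from exp(0.88) = 2.41 to exp(0.62) ≈ 1.85 at 30%. More daily smokers than 67 would raise the power but leave the attenuation as it is.

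**Step 4: the swab window.** At an approved site, a sample taken a week after Visit 3 would fall 7 of 21 days, one third, into Phase 4. This applies to that route only.

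**The case against.** The strongest reply is that the documents never say a late sample is analysed under the earlier dose. That is right. A reader might infer that next-dose samples will be counted as the previous dose, but the text supports only that they may be. The model is written in terms of dose rather than visit number, being near the visit can mean before it, and the label date would let an analyst find and reassign many late samples. The smartphone specimen reminders also continue in virtual mode, and the daily diary and timeline follow-back record product use. What remains is that no rule tells the analyst to use the date, and a label without a time cannot place a same-day sample before or after the switch.

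Two further readings go too far. A sample posted some days after the visit is not thereby late, because the rule governs collection, not shipping. And the one-week window does not cover all swabs: it applies to the approved-site route only, is pending approval, and serves an exploratory outcome.

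The size is also open to challenge. Only virtual visits are affected, and they are described as temporary. If half of Visit 3 contacts were virtual (an assumption), an overall share of 30% would need 0.30 / 0.50 = 60% of virtual samples to be late. The documents give no rate at which the biomarkers change after a switch, so full reflection of the new dose is an upper bound for a given share. At 30%, d_z of 0.37 still exceeds the minimum detectable 0.35 in Table 2. These points stand, and they limit the severity. They do not remove the bias toward zero.

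**Conclusion.** The concern holds for virtual visits only, as a moderate point and a cheap improvement. The stated windows themselves permit a compliant sample from the wrong side of the product switch, a single sample per virtual visit leaves nothing to replace it, and no assignment rule exists. The consequence for Aim 1 arises at Visit 3 and is attenuation: for daily smokers, from 0.88 to 0.79, 0.70 and 0.62 log units at assumed shares of 10%, 20% and 30%. Power stays at about 85% or more over that range, so the documents do not support a claim that the primary comparison loses its power unless late collection is common. The figures rest on the Table 1 means and SDs, a correlation of 0.4, n = 67, a two-sided 5% test, an assumed share, and late samples fully reflecting the new dose. Effects at Visits 1 and 2 and on the adduct concern exploratory aims.

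**What to change.** 1. In the COVID-19 adaptations under Sample collection and biomarker analyses and under Acrolein DNA Adduct (both the home and the site route), require collection on or shortly before the visit day and before first use of the next phase's product.
2. Record the date and time of collection and the time of first use of the new product.
3. In the Statistical Approach, pre-specify that samples taken after the switch, or after Visit 4, do not count toward the earlier phase in the TNE, minor-alkaloid and adduct analyses, and add a sensitivity analysis that includes them.
4. For samples already collected, apply the same rule using the label date together with the diary and timeline follow-back. Report how many samples are affected at each visit.

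The cost is instruction wording, two recorded times and a date check at analysis. The downside is that a few late samples drop out of the main analysis, and with one sample per virtual visit that means a missing phase value for those participants. The rule should be fixed before the data are analysed, since an exclusion chosen afterwards would be post hoc.
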